4.3.2.1 Supportive care guidelines for HFSR

At first occurrence of HFSR, independent of grade, prompt institution of supportive measures such as topical emollients, low potency steroids, or urea-containing creams should be administered.

Recommended prevention/management strategies for skin toxicities consistent with HFSR are summarized below:

4.3.2.1.1 **Control of calluses**

Before initiating treatment with regorafenib:

- Check condition of hands and feet.
- Suggest a manicure/pedicure, when indicated.
- Recommend pumice stone use for callus or 'rough spot' removal.

During regorafenib treatment:

- Avoid pressure points.
- Avoid items that rub, pinch or create friction.

4.3.2.1.2 **Use of creams**

- Non-urea based creams may be applied liberally.
- Keratolytic creams (e.g. urea-based creams, salicylic acid 6%) may be used sparingly and only to affected (hyperkeratotic) areas.
- Alpha hydroxyl acids (AHA) based creams may be applied liberally 2 times a day. Approximately 5% to 8% provides gentle chemical exfoliation.
- Topical analgesics (e.g. lidocaine 2%) are to be considered for pain control.
- Topical corticosteroids like clobetasol 0.05% should be considered for subjects with Grade 2 or 3 HFSR. Avoid systemic steroids.

4.3.2.1.3 **Tender areas should be protected as follows:**

- Use socks/gloves to cover moisturizing creams
- Wear well-padded footwear
- Use insole cushions or inserts (e.g. silicon, gel)
- Foot soaks with tepid water and Epson salts

4.3.3 **Management and Dose Modifications for Hypertension**

Hypertension is a known AE associated with regorafenib treatment. Subjects will have their blood pressure measured at least weekly at the study site during the first 6 weeks of treatment. If additional blood pressure measurements are done outside the study site, and the blood pressure is > 140 mm Hg systolic or > 90 mm Hg diastolic, then the subject will be instructed to contact study personnel. The management of hypertension, including the choice of antihypertensive medication, will be performed

according to local institutional standards and to the usual practice of the investigator. Every effort should be made to control blood pressure by medical means other than study drug dose modification. If necessary, Table 5 outlines

suggested dose reductions.

Table 5: Recommended Dose Modifications for Hypertension		
CTCAE v4.0 Grade	Antihypertensive Therapy	Regorafenib Dosing
Grade 1: Prehypertension (systolic BP 120 - 139 mmHg or diastolic BP 80 - 89 mmHg)	None	
 • Continue regorafenib • Consider increasing blood pressure (BP) monitoring
Grade 2: Systolic BP 140 - 159 mmHg or diastolic BP 90 - 99 mmHg OR Symptomatic increase by > 20 mmHg (diastolic) if previously within normal limits	
 • Treat with the aim to achieve diastolic BP ≤ 90 mm Hg: • If BP previously within normal limits, start anti-hypertensive monotherapy • If patient already on anti-hypertensive medication, titrate up the dose. 	
 • Continue regorafenib • If symptomatic, hold regorafenib until symptoms resolve AND diastolic BP ≤ 90 mm Hg^a. When regorafenib is restarted, continue at the same dose level.
Grade 3: Systolic BP ≥ 160 mmHg or diastolic BP ≥ 100 mmHg OR More than one drug or more intensive therapy than previously used indicated	Treat with the aim to achieve diastolic BP ≤ 90 mm Hg: Start anti-hypertensive medication AND/OR Increase current anti-hypertensive medication AND/OR Add additional anti-hypertensive medications.	
 • Hold regorafenib until diastolic BP ≤ 90 mm Hg, and if symptomatic, until symptoms resolve.^a • When regorafenib is restarted, continue at the same dose level. • If BP is not controlled with the addition of new or more intensive therapy, reduce by 1 dose level.^b • If Grade 3 hypertension recurs despite dose reduction and antihypertensive therapy, reduce another dose level.^c
Grade 4: Life-threatening consequences (eg, malignant hypertension, transient or permanent neurologic deficit, hypertensive crisis)	Per institutional guidelines	Discontinue therapy
a. Patients requiring a delay of > 4 weeks should go off protocol therapy b. If BP remains controlled for at least one cycle, dose re-escalation permitted per investigator's discretion. c. Patients requiring >2 dose reductions should go off protocol therapy.		

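### Table 5 (hypertension) is inconsistent in two limited cases: a Grade 3 hold entered on systolic pressure can be released at entry, and some treated patients fit both a continue row and a hold row

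*Combined protocol and SAP*

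**What the plan says.** Section 4.3.3 gives hypertension its own dosing table, Table 5. Table 2, the general toxicity table, excludes hypertension.

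- **Grade 3 entry.** Any one of three conditions is enough: systolic at or above 160, diastolic at or above 100, or a therapy condition that carries no pressure threshold, "More than one drug or more intensive therapy than previously used indicated".
- **Grade 3 release.** The dosing cell reads "Hold regorafenib until diastolic BP ≤ 90 mm Hg, and if symptomatic, until symptoms resolve". It contains no systolic value. Treatment then restarts at the same dose level.
- **Grade 2 entry.** "Grade 2: Systolic BP 140 - 159 mmHg or diastolic BP 90 - 99 mmHg OR Symptomatic increase by > 20 mmHg (diastolic"). The diastolic-rise limb applies where pressure was previously normal.
- **Grade 2 action.** The therapy cell says "If patient already on anti-hypertensive medication, titrate up the dose". The dosing cell says to continue regorafenib, with one exception: "If symptomatic, hold regorafenib until symptoms resolve AND diastolic BP ≤ 90 mm Hg".
- **Treatment aim.** Both rows use the same one: "Treat with the aim to achieve diastolic BP ≤ 90 mm Hg".

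The text above the table leaves management and the choice of drug to each site's standards and the investigator's usual practice. It presents Table 5 as suggested reductions for use where needed, and the table's title calls them recommended. The Grade 3 cell also gives later steps: reduce one dose level if pressure is not controlled on new or stronger therapy, and reduce again if Grade 3 recurs.

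**The concern.** A hold rule has two ends, and here they use different measurements. Systolic pressure alone can start the Grade 3 hold, but the only pressure that ends it is diastolic. A patient whose diastolic was never raised can therefore be told to stop and restart on the same reading.

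Separately, the Grade 3 therapy condition has no pressure threshold, and the Grade 2 row tells sites to increase antihypertensive treatment in patients already taking it. Following the Grade 2 instruction may itself satisfy the Grade 3 definition. The two rows then give opposite dosing instructions.

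At stake is whether sites apply the same dosing rule to the same patient. Section 4.3.3 names hypertension as a known adverse event of the drug, and later steps build on this table: the reductions, the re-escalation, and leaving protocol therapy after a delay of more than four weeks. Patients on antihypertensives can enrol, because exclusion 3.2.1 removes only those whose pressure is uncontrolled despite optimal management.

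**Working it through.** No sample-size or error-rate figure is involved. The check applies Table 5 as written to example readings.

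**Rules used (all from Table 5)**

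- Grade 3 by pressure: systolic ≥ 160 or diastolic ≥ 100.
- Grade 2 by pressure: systolic 140–159 or diastolic 90–99, and not Grade 3 by pressure.
- Grade 3 by therapy: stronger treatment than before is indicated. Titrating up is read as meeting this. The reading is an inference, supported by the Grade 3 therapy cell, which lists increasing the current medication among its actions.
- Release of a Grade 3 hold in an asymptomatic patient: diastolic ≤ 90.

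**Case 1: Grade 3 by pressure, asymptomatic**

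| Reading | Limb that triggers Grade 3 | Diastolic ≤ 90 at entry? | Effect of hold |
|---|---|---|---|
| 175/85 | systolic | yes | no duration |
| 165/85 | systolic | yes | no duration |
| 165/90 | systolic | yes | no duration |
| 165/95 | systolic | no | operates |
| 150/105 | diastolic | no | operates |

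The hold is empty only where systolic is at or above 160, diastolic is already at or below 90, and there are no symptoms. With symptoms, the hold lasts at least until they resolve.

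**Case 2: already on an antihypertensive, asymptomatic, Grade 2 by pressure**

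| Reading | Grade 2 row | Grade 3 row (therapy limb) | Conflict? |
|---|---|---|---|
| 145/92 | titrate up, continue | hold until diastolic ≤ 90 | yes |
| 150/95 | titrate up, continue | hold until diastolic ≤ 90 | yes |
| 150/85 | titrate up, continue | hold, already released | none in the initial action |

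If the same patient has symptoms, both rows hold until symptoms resolve and diastolic is at or below 90, and both restart at the same dose. There is no conflict. What remains is the asymptomatic treated patient with systolic below 160 and diastolic above 90 and up to 99.

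**Is there a tie-break?** Section 4.3.1 tells sites to follow the highest grade when a subject has more than one toxicity. That rule covers several toxicities, not one toxicity that fits two rows. Nothing in Table 5 or its footnotes settles the case.

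**How many patients?** The documents give no figure for either subset. Section 1.3.2 quotes grade 3 or higher hypertension of 7% in the colorectal trial and 48.5% in the GIST trial. Applied to 31 patients:

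- 0.07 × 31 = 2.2
- 0.485 × 31 = 15.0

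These are counts of all such events, not of the affected subset. They assume that both stages enrol fully and that rates from other tumours carry over. The two rates differ by a factor of 48.5 / 7 = 6.9.

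**The case against.** The strongest reply is that Table 5 is guidance, not a mandate. Section 4.3.3 puts management under local standards, asks sites to control pressure by means other than changing the study drug dose, and offers the table as suggestions. This stands and lowers the consequence. It does not say when a hold ends or which row governs, so it does not remove the inconsistency.

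The second reply is that the Grade 3 row has a backstop. It calls for antihypertensives to be started, increased or added, and for a dose reduction if pressure is not controlled; that wording is not confined to diastolic pressure. Section 4.8.1 also requires withdrawal if the investigator judges continuation harmful. This stands too. A reader might infer that a patient with severe systolic hypertension simply goes back on drug with nothing further done. The documents do not support that.

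Third, a reader might infer that every patient on baseline antihypertensives with a Grade 2 reading gets contradictory instructions. The second table above shows otherwise: symptomatic patients are held under both rows, and those with diastolic at or below 90 face the same initial action under both.

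Fourth, a reader might infer that reported rates of grade 3 or higher hypertension will not be comparable across sites. Sections 6.3, 7.2.2 and 7.3.2 grade adverse events by CTCAE v4.0, not by choosing a Table 5 row, so the documents do not establish that effect.

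Finally, the call-in rule in section 4.3.3 ("the blood pressure is > 140 mm Hg systolic or > 90 mm Hg diastolic") and exclusion 3.2.1 use both pressures, but one is a contact trigger and the other an entry criterion. Neither sets a release rule, so neither contradicts Table 5. A diastolic-only treatment aim is likewise a clinical choice. The mismatch lies within the table.

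**Conclusion.** The point holds in two limited cases, both internal to Table 5.

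1. An asymptomatic patient with systolic at or above 160 and diastolic already at or below 90 enters a Grade 3 hold whose release condition is already met. This follows directly from the text.
2. An asymptomatic patient already on an antihypertensive, with systolic below 160 and diastolic above 90 and up to 99, is told to continue by one row and to hold by another. This depends on reading titration as more intensive therapy, which the Grade 3 therapy cell supports but does not state.

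The size is unknown. A reader might take 2 to 15 of 31 patients as the number affected. That range counts all grade 3 or higher hypertension projected from two other trials, and the documents give no share for isolated systolic events or for treated patients in the overlap. No effect on the primary endpoint or on the two-stage decision has been shown. This is an inconsistency in advisory safety guidance that is worth correcting because it bears on when dosing stops and resumes.

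**What to change.** The sponsor should amend Table 5 in two places:

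- Reconcile the Grade 3 entry criteria with the Grade 3 release criterion, so that a hold cannot be over at the moment it begins.
- Reconcile the Grade 2 and Grade 3 rows for patients already on antihypertensives, so that one dosing instruction applies to a given patient. This should stay consistent with CTCAE v4.0 grading, not replace it.

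Which measurements, values and row should govern is a clinical decision for the sponsor; none is proposed here.

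The cost is a protocol amendment to one table. No new measurement is needed, because the blood pressure log in Appendix III already records systolic and diastolic pressure. The downside is that some holds may change in length.

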4.3.4 Liver Function Abnormalities

For patients with observed worsening of serum liver tests considered related to regorafenib (i.e. where no alternative cause is evident, such as post-hepatic cholestasis or disease progression), the dose modification and monitoring advice in Table 6 should be followed.

Regorafenib is a UGT1A1 inhibitor. Mild, indirect (unconjugated) hyperbilirubinemia may occur in patients with Gilbert's syndrome.

Table 6: Dose Modifications/Delays for Liver Function Abnormalities

Observed Elevations	1 st Occurrence	Restart	Re-occurrence
AST and/or ALT ≤ 5 X ULN (< G3)	Continue dosing, with weekly monitoring of liver function until transaminases return to <3 X ULN (≤ G1) or baseline.		
ALT and/or AST >5 X ULN (≥ G3)	Interrupt dosing, with weekly monitoring until transaminases return to < 3 X ULN or baseline.	If the potential benefit for reinitiating regorafenib is considered to outweigh the risk of hepatotoxicity: Reduce one dose level and measure serum liver tests weekly for at least 4 weeks.	Discontinue
ALT and/or AST > 20 X ULN (≥ G4)	Discontinue		
ALT and/or AST > 3 X ULN (≥ G2) with concurrent bilirubin > 2 X ULN	Discontinue treatment and measure serum liver tests weekly until resolution. Exception: patients with Gilbert's syndrome who develop elevated transaminases should be managed as per the recommendations outlined above for ALT/AST elevations.		

ALT, AST, and bilirubin must be monitored prior to initiation of regorafenib treatment. During the first 2 cycles (2 months) of treatment, ALT, AST and bilirubin will be monitored at least every 2 weeks.

4.3.5 Prevention/Management Strategies for Diarrhea

Diarrhea can be a common side effect of regorafenib. The preventive/management strategies for diarrhea should be consistent with local institutional standards (e.g., anti-diarrheals and optimized hydration status).

Anti-diarrhea medications may be introduced if symptoms occur. Previous trials have shown that the diarrhea could be managed with loperamide. The recommended dose of loperamide is 4 mg at first onset, followed by 2 mg every 2 to 4 hours until diarrhea-free for 12 hours.

4.4 PRIOR AND CONCOMITANT THERAPY

All medication that is considered necessary for the subject's welfare, and which is not expected to interfere with the evaluation of the study treatment, may be given at the discretion of the investigator. All medications (including contrast media) taken within 2 weeks prior to the start of the study and during the study must be recorded in the subject's source documentation and in the appropriate eCRF (including start/stop dates, dose frequency, route of administration, and indication).

Co-administration of a strong CYP3A4 inducer (rifampin) with a single 160 mg dose of regorafenib decreased the mean exposure of regorafenib, increased the mean exposure of the active metabolite M-5, and resulted in no change in the mean exposure of the active metabolite M-2. Avoid concomitant use of regorafenib with strong CYP3A4 inducers (e.g. rifampin, phenytoin, carbamazepine, phenobarbital, and St. John's Wort)

Co administration of a strong CYP3A4 inhibitor (ketoconazole) with a single 160mg dose of regorafenib increased the mean exposure of regorafenib and decreased the mean exposure of the active metabolites M-2 and M-5. Avoid concomitant use of regorafenib with strong inhibitors of CYP3A4 activity (e.g. clarithromycin, grapefruit juice, itraconazole, ketoconazole, nefazadone, posaconazole, telithromycin, and voriconazole).

4.4.1 Permitted Concomitant Therapies

- Standard therapies for concurrent medical conditions.
- Supportive care for any underlying illness.
- Palliative radiation therapy is allowed if the target lesion(s) are not included within the radiation field and no more than 30% of total bone marrow is irradiated to a total of 20 Gy (EQD2). Protocol treatment should be held 7 days before, during and 7 days after palliative radiation, or at the discretion of the site radiation oncologist. Palliative radiation cannot include target lesions.
- Palliative surgery: Protocol treatment should be held 7 days before and until the wound is healed. If treatment is not resumed within 3 weeks, the case will be reviewed by QAM and PI to determine whether or not subject can restart treatment. Palliative surgery cannot include surgery on target lesions.
- Granulocyte colony-stimulating factor (G-CSF) and other hematopoietic growth factors may be used in the management of acute toxicity, such as febrile neutropenia, when clinically indicated or at the investigator's discretion. However, they may not be substituted for a required dose reduction. Subjects are permitted to take chronic erythropoietin.

- Treatment with nonconventional therapies (such as acupuncture), and vitamin/mineral supplements are permitted provided that they do not interfere with the study endpoints, in the opinion of the investigator.
- Bisphosphonates
- Subjects who are prophylactically treated with an agent such as warfarin or heparin will be allowed to participate. Close monitoring (day 1 of each cycle) is mandatory. *NOTE: Therapeutic doses of anti-coagulants are not permitted.*

4.4.2 Concomitant Therapies Not Permitted:

- Other investigational treatment during study treatment.
- *Prior* use of sorafenib.
- Use of cytotoxic chemotherapy within 21 days of registration.
- Use of targeted therapy within two half-lives of registration.
- Radiation directed at target lesion within 28 days of registration.
- Concurrent systemic antitumor therapy, including cytotoxic therapy, signal transduction inhibitors, immunotherapy, and hormonal therapy.
- Bone marrow transplant or stem cell rescue.
- Subjects taking narrow therapeutic index medications should be monitored proactively (e.g. phenytoin, quinidine, carbamazepine, Phenobarbital, cyclosporin, and digoxin). *NOTE: Warfarin is metabolized by the cytochrome enzyme CYP2C9 and it's levels may be especially affected by regorafenib; therefore, only prophylactic doses of warfarin are permitted.*
- Use of drugs that induce CYP3A4 including (but not limited to):
 - Glucocorticoids (cortisone, hydrocortisone, prednisone, methylprednisone, dexamethasone)
 - Anticonvulsants (phenytoin, carbamazepine, phenobarbital, oxcarbazepine)
 - HIV antivirals (efavirenz, nevirapine)
 - Antibiotics (rifampin, rifabutin, rifapentine)
 - St. John's Wort
 - Modafinil
 - Pioglitazone

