- 3.2.17 History of organ allograft (including corneal transplant).
- 3.2.18 Known or suspected allergy or hypersensitivity to any of the study drugs, study drug classes, or excipients of the formulations given during the course of this trial.
- 3.2.19 Any malabsorption condition.
- 3.2.20 Evidence of abdominal fistula, GI perforation or intraabdominal abscess.
- 3.2.21 Women who are pregnant or breast-feeding.
- 3.2.22 Concurrent anti-cancer therapy (chemotherapy, surgery, immunotherapy, biologic therapy, or tumor embolization) other than study treatment (regorafenib).
- 3.2.23 Prior use of regorafenib.
- 3.2.24 Prior use of sorafenib.
- 3.2.25 Use of cytotoxic chemotherapy within 21 days of registration.
- 3.2.26 Use of targeted therapy within two half-lives of registration.
- 3.2.27 Radiation directed at target lesion within 28 days of registration.
- 3.2.28 Major surgical procedure, open biopsy, or significant traumatic injury within 28 days before registration.

3.2.29 Therapeutic anticoagulation with Vitamin-K antagonists (e.g., warfarin) or with heparins and heparinoids.

NOTE: Prophylactic anticoagulation as described below is allowed:

- Low dose warfarin (1 mg orally, once daily) with PT-INR $\leq 1.5 \times$ ULN is permitted. Infrequent bleeding or elevations in PT-INR have been reported in some subjects taking warfarin while on regorafenib therapy. Therefore, subjects taking concomitant warfarin should be monitored regularly for changes in PT, PT-INR or clinical bleeding episodes.
- Low dose aspirin (≤ 100 mg daily).
- Prophylactic doses of heparin.

3.2.30 Any condition which, in the investigator's opinion, makes the subject unsuitable for trial participation.

3.2.31 Substance abuse, medical, psychological or social conditions that may interfere with the subject's participation in the study or evaluation of the study results.

3.2.32 Unable or unwilling to discontinue use of strong inducers and inhibitors of CYP450 listed in Appendix for at least 14 days prior to the first dose of study treatment and for the duration of the study (Appendix A). CYP3A4 substrates can be administered, but investigators will need to be aware of possible increased or decreased effectiveness of the non-study drug and this should be recorded in concomitant medications. BCRP and PgP inducers and inhibitors should be used with caution if another alternative drug is not able to be used (Appendix A and B)

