6.1.3.1 Target lesion responses

Target lesions will be evaluated as follows:

- 6.1.3.1.1 **Complete response (CR):** Disappearance of all target lesions
- 6.1.3.1.2 **Partial response (PR):** $\geq 30\%$ decrease in the baseline sum diameters of target lesions
- 6.1.3.1.3 **Stable disease (SD):** Neither sufficient shrinkage to qualify for PR nor sufficient increase to qualify for PD, taking as reference the smallest sum diameters while on study
- 6.1.3.1.4 **Progressive disease (PD):** $\geq 20\%$ increase in the sum diameters of target lesions, taking as reference the smallest sum diameters while on study. The sum diameters must also demonstrate an absolute increase of 5 mm. The appearance of one or more new lesions also qualifies as PD.

6.1.3.2 Non-target lesions responses:

Non-target lesions will be evaluated as follows:

- 6.1.3.2.1 **Complete response (CR):** Disappearance of all non-target lesions with all lymph nodes < 10 mm in short axis.
- 6.1.3.2.2 **Non-CR/Non-PD:** Persistence of one or more non-target lesions
- 6.1.3.2.3 **Progressive disease (PD):** Unequivocal progression of non-target lesions (meriting discontinuation of regorafenib). The appearance of one or more new lesions also qualifies as PD.

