6.1.4 Evaluation of best overall response

The best overall response is the best response recorded from the start of the treatment until the end of treatment taking into account requirements for confirmation. Please refer to Table 8 below.

Table 7: Evaluation of Best Overall Response

Target Lesions	Non-Target Lesions	New Lesions	Overall Response
CR	CR	No	CR
CR	Non-CR/non-PD	No	PR
CR	Not evaluated	No	PR
PR	Non-PD or not all evaluated	No	PR
SD	Non-PD or not all evaluated	No	SD
Not all evaluated	Non-PD	No	Inevaluable
PD	Any	Yes or no	PD
Any	PD	Yes or no	PD
Any	Any	Yes	PD

Patients with a global deterioration of health status requiring discontinuation of treatment without objective evidence of disease progression at that time

should be classified as having “symptomatic deterioration.” Every effort should be made to document the objective progression, even after discontinuation of treatment.

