6.2 PRIMARY ENDPOINT ASSESSMENT

The primary endpoint of the study will be progression-free survival (PFS) at 4 months, defined as the absence of progression at 4 months. Patients must complete at least 2 cycles of study treatment to be considered evaluable for this endpoint.

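### Sections 4.4.1 and 6: palliative surgery or radiation to a non-target lesion can hide progression that was not yet documented, and no rule requires the lesion to be scored first

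*Combined protocol and SAP*

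**What the plan says.** **Local therapy on study.** Section 4.4.1 states that "Palliative radiation therapy is allowed if the target lesion(s) are not included within the radiation field", subject to a limit on irradiated bone marrow. It also permits palliative surgery, with the restriction that "Palliative surgery cannot include surgery on target lesions". It sets treatment holds around both, and review by the quality assurance monitor and the principal investigator if treatment has not resumed within 3 weeks of surgery. The antitumor treatment barred in 4.4.2 during the study is systemic: "Concurrent systemic antitumor therapy, including cytotoxic therapy, signal transduction inhibitors, immunotherapy, and hormonal therapy".

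**Eligibility.** Section 3.2.22 excludes "Concurrent anti-cancer therapy (chemotherapy, surgery, immunotherapy, biologic therapy, or tumor embolization) other than study treatment (regorafenib"). It names surgery, does not name radiation, and makes no palliative exception.

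**Progression.** Section 6.1.3.2.3 makes this PD: "Unequivocal progression of non-target lesions (meriting discontinuation of regorafenib"). A new lesion is also PD. In the 6.1.4 table, target SD or PR with no new lesion stays SD or PR when non-target lesions are "Non-PD or not all evaluated".

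**Endpoint and analysis.** The primary endpoint in 6.2 is "progression-free survival (PFS) at 4 months, defined as the absence of progression at 4 months". Section 6.3 counts progression or death as the PFS event. Section 9.4 names exponential and Kaplan-Meier methods. None of these sections mentions local therapy as an event, a censoring point or a reason for a sensitivity analysis.

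**The concern.** Section 4.4.1 protects the target lesions from local treatment, but target growth is only one of the routes to PD. Non-target progression is another. A non-target lesion that becomes troublesome between scheduled scans, which are 8 weeks apart (every 2 cycles), may be resected or irradiated before its growth is recorded. At the next assessment it is gone, altered or not evaluated. If the target lesions are stable and nothing new has appeared, the overall response is SD, and 6.2 counts the patient as progression-free.

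The trial has one arm and tests against a fixed null of 0.22, so no control group absorbs such misclassification. The samples are small: 12 patients in stage 1 and 31 in total. A single patient scored the wrong way moves stage 1 from 3 of 12 (stop) to 4 of 12 (continue).

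**Working it through.** **Step 1: follow the documents for one patient.** Target lesions are stable and there is no new lesion. One non-target lesion is treated locally before the 4-month assessment.

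- Growth documented as unequivocal before treatment: PD under 6.1.3.2.3, and PD overall in 6.1.4. Later local therapy does not undo it.
- Growth not documented before treatment: the lesion is afterwards recorded as absent or left unevaluated. Both fall in the same row of the 6.1.4 table, so overall response is SD, and the patient is a success under 6.2.

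The gap is the second case only.

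**Step 2: reproduce the plan's design.** Inputs from 9.3: n1 = 12, R1 = 3, n = 31, P0 = 0.22, P1 = 0.45. With X1 ~ Bin(12, p) and X2 ~ Bin(19, p):

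- PET = P(X1 ≤ 3)
- P(declare success) = Σ over x = 4 to 12 of P(X1 = x) · P(X2 ≥ R + 1 − x)
- Average N = 12 + (1 − PET) · 19

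At p = 0.22 and R = 10, PET = 0.739, average N = 12 + 0.261 · 19 = 16.96 and α = 0.047. At p = 0.45, power = 0.812, so β = 0.188. All four match the 9.3 table.

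The text of 9.3 instead requires more than 11 of 31 (R = 11), which gives α = 0.022 and power 0.752. That mismatch is a separate matter, so both rules are carried below.

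**Step 3: illustrate the effect.** Let f be the share of true 4-month failures scored as progression-free through this route. The documents give no value, so f is an assumption. The observed rate at a true rate of 0.22 is p = 0.22 + 0.78f. The expected number masked among 31 patients is 31 · 0.78 · f = 24.2f.

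| f | Masked patients in 31 | Observed p | Pass stage 1 (more than 3 of 12) | False positive, more than 10 of 31 | False positive, more than 11 of 31 |
|---|---|---|---|---|---|
| 0 | 0 | 0.220 | 0.261 | 0.047 | 0.022 |
| 2% | 0.5 | 0.236 | 0.307 | 0.071 | 0.036 |
| 5% | 1.2 | 0.259 | 0.379 | 0.122 | 0.069 |
| 10% | 2.4 | 0.298 | 0.501 | 0.245 | 0.160 |

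**Step 4: price the strict remedy.** Suppose every locally treated patient were a failure in the Simon decision itself, and that this reclassified a share g of true successes at p = 0.45 (again an assumption). Then p = 0.45(1 − g).

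| g | p | Power, more than 10 of 31 | Power, more than 11 of 31 |
|---|---|---|---|
| 0 | 0.450 | 0.812 | 0.752 |
| 5% | 0.4275 | 0.749 | 0.674 |
| 10% | 0.405 | 0.675 | 0.585 |

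**The case against.** The best defence is that the plan already catches most such patients. Unequivocal non-target progression and new lesions are PD whatever follows. Assessment is not confined to the 8-weekly scans: physical examination is scheduled every cycle, footnote d in Section 5.0 refers to imaging as clinically indicated and to visual measurement, and 6.1.1 accepts calipers for superficial lesions. A lesion bad enough for surgery or radiation would plausibly be examined or imaged first. To be masked, a patient must have progression in non-target lesions only, have it treated before documentation, and then reach 4 months without target progression or a new lesion. That may be rare.

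This stands as a limit on size. It does not close the gap, because no section requires the pre-procedure findings to be scored under 6.1.3.2 or says how the treated lesion is handled afterwards.

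A reader might also infer that 3.2.22 and 4.4.1 flatly contradict each other on both surgery and radiation. The documents do not support that. Section 3.2.22 is an eligibility criterion, 4.4.1 governs care on study, and 3.2.22 does not list radiation. What remains is unreconciled wording on surgery.

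Finally, counting every locally treated patient as a failure in the primary decision would penalise palliation of lesions that have not progressed, and it departs from PFS as defined in 6.3. Step 4 shows that the loss of power could be material, so that rule belongs in a sensitivity analysis.

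**Conclusion.** The point holds in a limited form. Because pre-procedure assessment is not required and unevaluated non-target lesions leave SD or PR intact, non-target progression treated before it is documented can be scored as a success for the primary endpoint. It would be wrong to infer that any patient whose growing non-target lesion is removed or irradiated stays progression-free: once growth is documented as unequivocal, or a new lesion appears, the patient is PD.

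The size is illustrative and rests on the assumed f. At 5%, about 1.2 patients in 31, the false-positive probability rises from 0.047 to 0.122 under the table rule and from 0.022 to 0.069 under the text rule. At 2% it reaches 0.071 or 0.036. These figures show how sensitive a small single-arm test is to one or two misclassified patients. They are not estimates of the error in this trial.

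**What to change.** - **6.2 and 6.3:** state that, before palliative surgery or radiation to a tumour lesion, its status is scored under 6.1.3.2 from the available treatment-planning or preoperative imaging or examination, and that PD is recorded at that date if the criteria are met.
- **6.1.4 table:** state that a lesion unevaluated, or recorded as absent, because of local therapy does not lead by default to SD or PR unless that pre-procedure assessment exists.
- **9.4:** add a sensitivity analysis that counts patients given tumour-directed local therapy before the 4-month assessment as failures, shown beside the primary result.
- **3.2.22 and 4.4.1:** reconcile the wording on surgery, making clear which text governs eligibility and which governs care on study.

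The permission for palliative care does not need to change for this purpose. The cost is a few sentences and one eCRF field for the pre-procedure lesion status and date. The reported 4-month rate may be slightly lower, because some progression that would have gone unrecorded will be counted.
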